
Drugs, Dosages, and Regimens

Baseline visit will consist of all evaluations. For subjects who meet inclusion/exclusion criteria, they will be randomized at the end of their baseline visit.

All 80 subjects who are randomized to Vortioxetine (1:1 randomization) will receive 10mg/day or placebo during the first week of the study (the first dose will be started the day immediately after the baseline visit). All subjects will receive 10mg or placebo for 7 days and then will be evaluated with all measures at week 1 (7 days after baseline).

At the week 1 visit, subjects will be started on 20mg/day (or remain on placebo) for the remainder of the study. They will return at week 2 (corresponding to having been on 20mg/day for one week) and be evaluated with all measures. After week 2 visit, all subjects will be seen every two weeks for the remainder of the 12-week study period (this corresponds to visits at week 4, 6, 8, 10, and 12). Week 12 evaluation will be the study endpoint for purposes of efficacy.

All visits are as outpatients and include in-person assessments.

After study conclusion (at week 12), the dose will be tapered off during a 1-week follow-up period. All subjects will return at week 13 for final safety evaluation only.

Dosage changes/reductions will not be permitted. Because nausea, and possibly headache, are the most likely side effects anticipated at the 20mg dose, participants will be allowed the use of over-the-counter options such as Tylenol prn for headaches, or bismuth subsalicylate for nausea. The use of over-the-counter options will be tracked at each visit. If side effects continue and are intolerable, the participant will have to discontinue treatment. If that occurs, a detailed 'final visit' assessment will be conducted and the participant will be contacted two weeks following to assess side effect outcomes.

Treatment Duration, Visit Frequency, and Procedures

This is a 13-week study (12 weeks of acute treatment followed by a 1-week tapering phase). Subjects will be seen for a total of 9 study visits. All visits will include the full battery of assessments except week 13 which is only a safety evaluation.

Randomization

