Weight will be recorded using a calibrated scale with the participants not wearing shoes, rounded to the nearest 0.5 pounds, and converted to kilograms (to convert, multiply by 0.45) for data reporting.

Following-Up Visit Assessments

All follow-up visits will include safety measures (adverse events, vital signs, C-SSRS), weight, binge eating measures, Clinical Global Impressions–Improvement Scale, and other psychiatric measures.

Medical evaluation including physical examination will be performed again at study endpoint.

At study completion, participants will be made aware of all available options for follow-up care in the community.

Safety Assessments

Safety and tolerability will be assessed using spontaneously reported adverse events data, Columbia–Suicide Severity Rating Scale (C-SSRS) vital signs, and by evaluating premature termination. Safety assessments (C-SSRS, sitting blood pressure, heart rate, adverse effects, and concomitant medications) will be documented at each visit.

Subjects who are an immediate suicide risk will be removed from the study and appropriate clinical intervention (e.g. hospitalization) will be arranged. Urine pregnancy tests will be performed at the initial visit. Subjects who have a positive urine pregnancy test will be excluded from the study. Assessment of side effects will be done at each visit. AEs will be coded by system organ class (SOC) and preferred term (PT) using the Medical Dictionary for Regulatory Activities (Med- DRA) Version11.1. The incidences of all AEs will be summarized descriptively.

Safety Reporting (please do not change the safety section of the template)

Institution/Investigator is solely responsible for reporting all Adverse Events and Serious Adverse Events to regulatory authorities, investigators, IRBs or IECs and Takeda, as applicable, in accordance with national regulations in the countries where the study is conducted.

Regardless of expectedness or causality, all SAEs and pregnancy reports must also be reported in English by facsimile to Takeda Pharmacovigilance or designee:

Fatal and Life Threatening SAEs within 24 hours of the sponsor-investigator's observation or awareness of the event

All other serious (non-fatal/non-life threatening) events within 4 calendar days of the sponsor-investigator's observation or awareness of the event

Takeda Safety Reporting Contact Information

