A medication error is a preventable event that involves an identifiable patient and that leads to inappropriate medication use, which may result in patient harm. While overdoses and underdoses constitute medication errors, doses missed inadvertently by a patient do not. Individuals who identify a potential medication error situation should immediately contact Takeda (see below) and report the event.

Phone: [name] ([name])

E-mail: [contact]

[contact]

Product complaints and medication errors in and of themselves are not AEs. If a product complaint or medication error results in an SAE, an SAE form should be completed and sent to Takeda Pharmacovigilance.

Statistical Analysis:

Design/Randomization

The study is a double-blind, placebo-controlled study. Participants will be randomized (1:1) to receive vortioxetine or placebo by the University of Chicago Investigational pharmacy in block sizes of eight, using computer-generated randomization with no clinical information.

Efficacy Analysis

For statistical analysis, the full-analysis set will be defined as all participants who took at least 1 dose of the study drug and had at least 1 post-baseline primary efficacy assessment. The safety-analysis set will be defined as all randomized participants who took at least 1 dose of the study drug and completed at least 1 follow-up safety assessment.

We will compare the baseline characteristics of both groups using Fisher's exact test for categorical variables and the t test for continuous variables. We will calculate adherence to treatment, based on the number of capsules returned at each visit, as the number of capsules taken divided by the number of days in the study \times 100%.

Primary endpoint analysis

The primary outcome measure will be the change from baseline in frequency of binge eating episodes (binges/week), defined as the mean number of binges per week in 2-week intervals. If the visit interval is less than 2 weeks, the mean number of binges per week will be estimated based on the number of binge days in the interval since the last visit.

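### Low priority: the only safety set defined requires a completed follow-up assessment, so a dosed participant lost before one would drop out of adverse event incidence even if an event is known

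*Combined protocol and SAP*

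**What the plan says.** The analysis sets are defined under Statistical Analysis, Efficacy Analysis. The safety-analysis set is all randomised participants who "took at least 1 dose of the study drug and completed at least 1 follow-up safety assessment". Both conditions must be met.

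The timing comes from Drugs, Dosages, and Regimens. There, "the first dose will be started the day immediately after the baseline visit", and the first scheduled follow-up is the week 1 visit, 7 days after baseline. For a participant who stops because side effects are intolerable, a final visit "assessment will be conducted and the participant will be contacted two weeks following to assess side effect outcomes".

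Safety Assessments ties safety data to visits ("Assessment of side effects will be done at each visit") and also relies on spontaneous reports of adverse events. On analysis it says "The incidences of all AEs will be summarized descriptively". The Safety analyses section adds a Fisher exact comparison of treatment-emergent adverse event incidence between groups. Neither place names an analysis set.

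Reporting to the company does not depend on visits. Under Safety Reporting, "Regardless of expectedness or causality, all SAEs and pregnancy reports must also be reported in English by facsimile to Takeda Pharmacovigilance or designee", with time limits that run from the sponsor-investigator's "observation or awareness of the event".

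**The concern.** A safety set normally includes everyone exposed. This one adds a condition that a participant can fail because of the outcome that the set is meant to count. The definition of an SAE includes death and inpatient hospitalisation, and either could prevent attendance at week 1. No sentence returns such a person to the set when the event is known by another route.

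Safety is part of the primary aim. With 40 per arm, a serious event may well be a single case, so omitting one known case can remove it from the incidence table altogether. What is at stake is the completeness of that table. The plan attaches no decision rule to adverse events, so no formal conclusion depends on the Fisher p-value.

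**Working it through.** **What the text implies**

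1. Membership of the safety set needs randomisation, at least one dose, and at least one completed follow-up safety assessment.
2. Dosing starts the day after baseline and the first scheduled assessment is at week 1, so a participant can be dosed and not yet qualify.
3. Anyone who attends week 1, any later visit or a final visit has qualified. The gap is therefore confined to people with no follow-up safety assessment at all.
4. An event in such a person can still become known, because SAE reporting starts from awareness and adverse events may be reported spontaneously.
5. No denominator is named for the summary or the Fisher test. That the safety set is meant is an inference from its being the only safety population defined.

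**Size, on assumed counts**

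The plan states no figure to reproduce here. The only input from the documents is 40 per arm. The event counts x are assumptions, because no early-loss rate or adverse event rate is given.

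*One participant with the event is excluded.* The arm's rate changes by (x−1)/39 − x/40 = (x−40)/1560.

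*One silent loss is counted as event-free instead of being left out* (the cost of the fix). The rate falls from x/39 to x/40, a drop of x/1560.

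| Assumed x of 40 | One known event excluded | One silent loss counted as event-free |
|---|---|---|
| 1 | 1/40 to 0/39: −2.50 points | −0.06 points |
| 9 | 9/40 to 8/39: −1.99 points | −0.58 points |
| 15 | 15/40 to 14/39: −1.60 points | −0.96 points |

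The two are equal in size when 40 − x = x, that is at 20/40. Below 50% incidence, one excluded known event moves the rate more than one silent loss does. How many of each would occur is unknown.

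**Fisher exact test, two-sided, same assumptions.** Participants with the event are removed from the arm with more events.

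| Base case | No exclusion | One excluded | Two excluded | Three excluded |
|---|---|---|---|---|
| 6/40 v 4/40 | 0.74 | 0.74 | 1.00 | not run |
| 9/40 v 2/40 | 0.048 | 0.048 | 0.083 | not run |
| 15/40 v 5/40 | 0.019 | 0.019 | 0.032 | 0.053 |
| 1/40 v 0/40 | 1.00 | 1.00 | – | – |

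One such exclusion leaves p unchanged in all four cases. That result depends on which arm loses the person. Removing one event from the arm with fewer events gives p = 0.48 for 6/40 v 3/39, 0.014 for 9/40 v 1/39 and 0.0075 for 15/40 v 4/39. Leaving out an event-free participant from the arm with more events (9/39 v 2/40) gives p = 0.025. The movement can therefore go either way. With no exclusions, nothing changes.

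**The case against.** The strongest reply has four parts.

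- **The denominator is inferred.** This is right: neither the descriptive summary nor the Fisher test names a set. If the safety set is not meant, the denominator is unspecified, and the same edit settles it.
- **A follow-up safety assessment is not defined exactly.** Adverse effects are one listed component, and the contact two weeks after a final visit, or a documented contact about an event, might be taken to count. This stands as an ambiguity. The requirement that an assessment be completed, and the statement that assessments are documented at visits, point the other way.
- **Known events are handled elsewhere.** A reader might infer that an early serious event would go unreported. The documents do not support that. SAEs go to the company, other adverse events go into the annual progress reports, adverse drug reactions go into the final study report, and the PI prepares written summaries of adverse events. None of this puts the person back in the safety set, so only the incidence summary and the test are affected.
- **The group is small.** A reader might also infer that people who stop for intolerable side effects are dropped from the safety analysis. They are not, if they attend the final visit or have attended any follow-up visit. Sample Size expects few drop-outs, though it gives no rate.

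A lighter remedy would be a footnote listing, by arm, events in dosed participants outside the set. It would disclose the events but leave the incidence and the test without them.

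**Conclusion.** The point holds as a low-priority, cheap improvement. As written, the rule can exclude a dosed participant with a known event, and on the natural reading that person would be missing from the adverse event incidence and the Fisher test.

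It is tempting to go further and say that the rule understates harm on vortioxetine or biases the comparison. The documents do not support that. They give no count of early losses, no event rate and no reason to expect the losses in one arm rather than the other. The illustration of 2.5% becoming 0% rests on an assumed single event among 40. The conclusion depends on the safety set being the intended denominator and on a follow-up safety assessment meaning one completed at a visit.

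**What to change.** - Define the safety set as all randomised participants who received at least one dose, with no condition on follow-up.
- Count adverse events known from any source, from first dose.
- Name this set as the denominator for both the descriptive incidence summary (Safety Assessments) and the Fisher test (Safety analyses).
- Report by arm the number dosed, or with dosing unknown, who had no follow-up safety assessment. The unknown category is needed because intake is worked out from capsules returned at visits, which says nothing about a person who never comes back.

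The cost is a few sentences and no new data collection. The downside is that a person lost without any report counts as event-free, which lowers that arm's rate by the 0.06 to 0.96 points shown above. The per-arm count lets a reader see how far this could matter.

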Rationale for evaluating this compound in this population/target organ. Provide overall reason the study is being proposed, including past study results that may have led to a decision to propose this study.

Vortioxetine has distinctive properties that make it a promising option for patients with

binge eating disorder. In vitro studies indicate that vortioxetine is an inhibitor of the 5-HT transporter and is a 5-HT1D, 5-HT3 and 5-HT7 receptor antagonist, a 5-HT1A receptor agonist and a 5-HT1B receptor partial agonist. Animal and in vitro studies indicate that several neurotransmitter systems may be impacted by vortioxetine, with the drug enhancing levels of 5-HT, noradrenaline, dopamine, acetylcholine and histamine in certain areas of the brain, as well as modulating γ -aminobutyric acid and glutamate neurotransmission (Gibb and Deeks, 2014). In addition, vortioxetine appears to improve executive functioning which in turn has the potential to improve top-down cognitive control (Mahableshwarkar et al., 2015). This suggests that vortioxetine could improve the symptoms of binge eating disorder by two complementary pathways. Finally, because of low rates of side effects, low likelihood of sexual dysfunction, and the potential for improved cognitive performance, vortioxetine should be a well-tolerated and in fact desired medication approach to binge eating.

Given the serious public health problems associated with binge eating disorder, and the likelihood of success of vortioxetine in treating the disorder, the aim of the present study was to examine the efficacy and safety of vortioxetine vs placebo in adults with moderate to severe Binge eating disorder, as indicated by at least 3 binge eating days per week for the 2 weeks before the baseline visit

Hypothesis:

State hypothesis for study objectives.

We hypothesize that vortioxetine will be more effective than placebo in reducing the number of binge eating days per week after 12 weeks of treatment when compared to baseline.

Primary Aim/Objective:

For clinical studies– eg, To evaluate the safety and efficacy of interventions with test medication on symptoms, signs and quality of life in patients with target condition.

The aim of the present study is to examine the efficacy and safety of vortioxetine vs placebo in adults with moderate to severe Binge eating disorder, as indicated by at least 3 binge eating days per week for the 2 weeks before the baseline visit.

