Secondary Aim/Objective: *(if applicable)*

A secondary aim of the study is to examine the effects of vortioxetine vs placebo on overall functioning and quality of life.

Primary Endpoint(s):

The primary efficacy measure is the number of binge eating days per week based on clinician interview and confirmation of identified Binge eating episodes in self-reported Binge eating diaries. The primary efficacy end point is the change from baseline to week 12 on the log-transformed scale (Binge eating days per week) + 1.

Secondary Endpoint(s): (if applicable)

Secondary efficacy measures include the number of Binge eating episodes per week, 1-week Binge eating episode response status, and 4-week cessation from Binge eating (free from Binge eating episodes). Other secondary endpoints include the change in weight/BMI between baseline and study endpoint, the Clinical Global Impressions–Improvement Scale (CGI-I) rated global improvement of symptoms over time (results will be dichotomized as improved [CGI-I ratings of 1 or 2 very much/much improved] or not improved [CGI-I ratings of 3-7]). The self-reported Eating Inventory, also known as the Three-Factor Eating Questionnaire, the self-reported Binge Eating Scale, the Yale-Brown Obsessive Compulsive Scale modified for Binge Eating (YBOCS-BE), the Quality of Life Inventory, the Hamilton Depression Rating Scale and the Hamilton Anxiety Rating Scale.

Study Plan:

Eighty individuals with binge eating disorder will be recruited for a double-blind, placebo-controlled pilot study in which Vortioxetine or placebo is administered in a 1:1 fashion. All 80 subjects will have binge eating disorder per DSM-5 criteria for at least a year. Following baseline measures, subjects will receive Vortioxetine (10mg for one week and then 20mg thereafter) or inactive placebo. Participants will be seen one week after the baseline visit (assessing the 10mg dose), one week after that (assessing the 20mg dose), and then every 2 weeks for the remainder of the 12-week period. At week 12, subjects will start a 1-week taper off the medication and will be seen at week 13. Efficacy and safety measures will be performed at each visit.

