Between group comparisons will use a mixed-effects model for repeated measures, including fixed factors for treatment and visit, the interaction of treatment and visit, a covariate of the log-transformation ([baseline number of BE days per week] + 1), and the interaction of the baseline covariate and visit using visit as a categorical variable. Mixed-effects models for repeated measures estimates differences from placebo in the change from baseline of the log-transformed scale ([BE days per week] + 1) at week 12 (primary end point). Based on previous research, log-transformation should reduce skewness (McElroy et al., 2007).

Secondary endpoints analyses

Secondary outcome measures will include the change from baseline in frequency of binge days (or mean days per week when the participant had one or more binges), weight, body mass index, global improvement, Three-Factor Eating Questionnaire, and Impact of Weight on Quality of Life.

We will also analyze changes from baseline in log-transformed BE episodes, TFEQ factor scores, and YBOCS-BE total score to week 12 using the mixed-effects model for repeated measures. Pairwise χ^2 statistical tests will evaluate dichotomized CGI-I ratings at week 12 for placebo vs treatment group.

Response categories will be tabulated based on the percentage decrease in frequency of binges from baseline to endpoint, which will be defined as follows: complete=cessation of binges; marked=75% to <100% decrease; moderate=50% to <75% decrease; and none=<50% decrease.

We will calculate effect sizes for the primary analysis of binges per week and weight using Cohen's d. Finally, we will perform a Spearman rank correlation to assess the association between the change in frequency of binges from baseline to week 12 and the change in weight from baseline using completers.

Safety analyses

Adverse events will be collected at baseline visit. We will evaluate differences between groups in the incidence of treatment-emergent adverse events using Fisher's exact test. Descriptive statistics will be used to evaluate changes in laboratory values, blood pressure and heart rate.

Sample Size

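### The plan names two different primary outcomes: binge-eating days per week in the hypothesis, endpoint section, model and sample size, but binge episodes per week where the primary endpoint analysis defines it

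*Combined protocol and SAP*

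**What the plan says.** Places where days per week is the main outcome:

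- **Hypothesis:** "vortioxetine will be more effective than placebo in reducing the number of binge eating days per week after 12 weeks of treatment".
- **Primary Endpoint(s):** "The primary efficacy measure is the number of binge eating days per week", followed by the change to week 12 on the log scale as the end point.
- **Statistical Analysis, Primary endpoint analysis (the model):** treatment differences are estimated "in the change from baseline of the log-transformed scale ([BE days per week] + 1) at week 12 (primary end point"), with log baseline days as the covariate.
- **Sample Size:** the calculation is for change in days per week on the log scale, with an effect size of 0.6 to 0.7, 80% power and 40 per arm.

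Places where episodes per week is primary, or days is secondary:

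- **Statistical Analysis, Primary endpoint analysis (opening sentence):** "The primary outcome measure will be the change from baseline in frequency of binge eating episodes (binges/week"), further defined as a weekly mean over 2-week intervals.
- **Secondary endpoints analyses:** the frequency of binge days is in the secondary list, and the Cohen's d sentence speaks of a primary analysis of binges per week and weight.

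Places where episodes per week is secondary:

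- **Secondary Endpoint(s):** "Secondary efficacy measures include the number of Binge eating episodes per week".
- **Secondary endpoints analyses:** log-transformed episodes are among the further mixed-model analyses.

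For visit intervals shorter than 2 weeks, Primary endpoint analysis adds that "the mean number of binges per week will be estimated based on the number of binge days in the interval" since the last visit.

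**The concern.** Days and episodes are different variables. The plan itself describes a binge day as one containing one or more binges, so a participant can halve the episodes without changing the number of days. The subsection that should settle the matter defines one variable and then models the other.

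Two things are at stake. First, a report could present either variable as primary and cite the plan in support. The .05 level, the effect size and the power were set for days, and the documents give no effect size or standard deviation for episodes, so an episodes primary would have no stated power basis. Second, if episodes were used, the short-interval rule would change what is counted between the early visits and the later ones.

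**Working it through.** **1. What the sample size supports.** Inputs from Sample Size: effect size d = 0.6 to 0.7, power 80%, 2-group t test, level .05. Sidedness is not stated; two-sided is assumed. The exact noncentral t calculation gives:

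| d | n per arm for 80% power | power with 40 per arm |
|---|---|---|
| 0.60 | 45 | 75.5% |
| 0.65 | 39 | 81.9% |
| 0.70 | 34 | 87.1% |

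Forty per arm gives 80% power at d = 0.634, inside the stated range. A one-sided test would need 36, 30 and 26, none of which matches 40. The stated figure therefore reproduces for days, though not at the lower end of the range. No equivalent calculation is possible for episodes.

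**2. Role of each variable, by section.**

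| Section | Days per week | Episodes per week |
|---|---|---|
| Hypothesis | tested outcome | – |
| Primary and Secondary Endpoint(s) | primary | secondary |
| Primary endpoint analysis, opening | – | primary |
| Primary endpoint analysis, model | primary | – |
| Secondary endpoints analyses, list | secondary | – |
| Secondary endpoints analyses, further models | – | secondary |
| Secondary endpoints analyses, Cohen's d | – | primary (on its natural reading) |
| Sample Size | primary | – |

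Each variable is primary in at least one place and secondary in at least one other. No sentence ranks the sections.

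**3. False-positive risk if either could be called primary.** Let Z1 and Z2 be the two test statistics under no effect, bivariate normal with correlation ρ. The risk is 1 − P(|Z1| < 1.96 and |Z2| < 1.96). The documents give no ρ, so a range is assumed:

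| ρ | risk |
|---|---|
| 0.50 | 1 − 0.9093 = 9.1% |
| 0.70 | 1 − 0.9165 = 8.3% |
| 0.80 | 1 − 0.9219 = 7.8% |
| 0.90 | 1 − 0.9296 = 7.0% |
| 0.95 | 1 − 0.9354 = 6.5% |
| 0.98 | 1 − 0.9407 = 5.9% |

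With one primary fixed in advance the risk is 5%.

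**4. Short-interval rule.** Study Plan sets the first two visits a week apart: "Participants will be seen one week after the baseline visit (assessing the 10mg dose), one week after that (assessing the 20mg dose"). Drugs, Dosages, and Regimens continues: "After week 2 visit, all subjects will be seen every two weeks for the remainder of the 12-week study period". The post-baseline efficacy visits are therefore weeks 1, 2, 4, 6, 8, 10 and 12. Scheduled intervals shorter than 2 weeks end at weeks 1 and 2, which is 2 of 7.

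Read the rule as one binge per binge day, and take an unchanged participant with 4 binge days per week and k binges per binge day (both assumed). True binges per week are 4k, the recorded value is 4, and the apparent change is (4 − 4k)/(4k):

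- k = 1.25: (4 − 5)/5 = −20%
- k = 1.5: (4 − 6)/6 = −33%
- k = 2: (4 − 8)/8 = −50%

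Week 12 follows a scheduled 2-week interval and is not directly affected.

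**The case against.** The best reply is that the intent is clear. Wherever a sentence identifies the primary end point by that term, it is days; the conflicting sentence uses a different term, outcome measure. Hypothesis, endpoint, model, covariate and power all agree. This makes days the likely intent, but it does not remove the contradiction: the opening sentence defines its variable in full, and the secondary list then places days among the secondary outcomes, so more than one stray word is involved.

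The Cohen's d sentence is weaker evidence. It couples binges per week with weight, which is secondary throughout, so "primary analysis" there may only mean the main analysis of each variable. The finding does not need it.

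The false-positive figures depend on an assumed correlation and on a two-sided test. They apply only if the primary is chosen after the results are seen, which nothing in the documents suggests. They are an upper illustration and not a forecast.

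The 20% to 50% apparent falls need three conditions: episodes as the outcome, one binge counted per binge day, and an assumed k. The same rule applies in both blinded arms, so the fall within a participant is not in itself a bias in the treatment comparison. That illustration is a side issue.

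**Conclusion.** The concern holds and should be corrected before the data are unblinded. The primary outcome carries the trial's .05 test and its sample size, and the plan does not define it uniquely. This rests on the text alone and needs no assumption.

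The sizes are illustrative. The false-positive risk would be 7.0% to 8.3% instead of 5% for correlations of 0.9 down to 0.7, only if the choice were left open until the results were known. The short-interval rule matters at 2 of 7 visits, and only for an episode count. The sample size is not wrong on this account: 40 per arm is consistent with an outcome based on days.

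**What to change.** Make the change from baseline to week 12 in log(binge-eating days per week + 1) the only primary outcome, and edit four places:

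1. **Primary endpoint analysis, definition and short-interval rule.** Replace both sentences with, for example: *The primary outcome is the change from baseline to week 12 in log([binge-eating days per week] + 1). Binge-eating days per week is the number of days with one or more binges in the 2-week interval before the visit, divided by the days in that interval, times 7. If the visit interval is shorter than 2 weeks, the days since the last visit are used as the interval.* Cross-refer to Primary Endpoint(s), so that clinician interview and diary confirmation still apply.
2. **Secondary endpoints analyses, list.** Delete the frequency of binge days.
3. **Same list.** Name episodes per week, counted as episodes at every visit. This agrees with Secondary Endpoint(s) and with the log-episodes model already planned.
4. **Cohen's d sentence.** Replace binges per week with log binge-eating days per week.

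Data collection, visits, model and sample size do not change. The cost is a dated amendment before unblinding, with the written approvals sent to the funder as Ethical and Regulatory Considerations requires, and a check that the registered primary outcome matches. Choosing episodes instead would cost more: the model, the baseline covariate and the sample size would all have to be restated with an episode-based effect size.

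### The plan names two different primary variables, binge episodes and binge days per week, and its short-interval rule mixes the two units

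*Combined protocol and SAP*

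**What the plan says.** All references are to the combined protocol and SAP.

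**Places that make binge days primary**
- Hypothesis: "We hypothesize that vortioxetine will be more effective than placebo in reducing the number of binge eating days per week".
- Primary Endpoint(s): "The primary efficacy measure is the number of binge eating days per week based on clinician interview", together with "confirmation of identified Binge eating episodes in self-reported Binge eating diaries". The end point is the change to week 12 in log(binge days per week + 1). Secondary Endpoint(s) then lists episodes per week as secondary.
- Primary endpoint analysis, model paragraph: both the baseline covariate and the response are log(binge days per week + 1), and the week 12 contrast is labelled the primary end point.
- Sample Size: the calculation is for binge days per week on the log scale.

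**Places that make episodes primary**
- Primary endpoint analysis, opening paragraph: "The primary outcome measure will be the change from baseline in frequency of binge eating episodes (binges/week"), averaged over 2-week intervals.
- Secondary endpoints analyses: binge days appear as a secondary outcome, described as "mean days per week when the participant had one or more binges". The same section says "We will calculate effect sizes for the primary analysis of binges per week". It also says "We will also analyze changes from baseline in log-transformed BE episodes", which treats episodes as a further, non-primary analysis.

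**The short-interval rule**

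For visits less than 2 weeks apart, "the mean number of binges per week will be estimated based on the number of binge days in the interval since the last visit". No formula or conversion follows.

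**The concern.** A confirmatory comparison needs one primary variable, fixed in advance. Here the heading that should settle the matter opens with one variable and models another, and the next section sides with the opening paragraph. An analyst could defend either choice after unblinding, so the nominal 5% error rate is not protected. The justification for 40 per arm covers only one of the two.

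The short-interval rule adds a smaller problem. A binge day is a day with at least one binge, so the number of binge days can never exceed the number of binges and falls below it whenever a day holds two or more. Using days to stand for binges at some visits and counting binges at others puts two units into one outcome series. At stake there are the early time course of episodes and any episode value taken at a final visit soon after the previous one.

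**Working it through.** **1. The plan's own figure.** Inputs from Sample Size: effect size 0.6 to 0.7, 80% power, two-group t test at the .05 level, 40 per arm. Sidedness is not stated; I assume two-sided.

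| Effect size | n per arm for 80% power | Power at 40 per arm |
|---|---|---|
| 0.60 | 45 | 75.5% |
| 0.65 | 39 | 81.9% |
| 0.70 | 34 | 87.1% |

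Forty per arm gives 80% power at an effect size of 0.634, inside the stated range, so the figure reproduces. It was derived for binge days. The plan gives no effect size or standard deviation for episodes, so no corresponding number can be computed for them.

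**2. Which variable is primary.** Four places use days: the hypothesis, the endpoint section, the model and the sample size. Three statements side with episodes: the opening of the primary endpoint analysis, the listing of binge days as secondary, and the effect-size sentence.

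As an illustration of what an open choice costs, suppose there is no treatment effect, each variable is tested two-sided at 0.05, and either result may be called primary. With bivariate normal test statistics, the chance that at least one is significant is 0.070 at a correlation of 0.9 and 0.083 at 0.7. Both correlations are assumed; the documents give none.

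**3. Where the short-interval rule applies.** Drugs, Dosages, and Regimens sets visits at weeks 1, 2, 4, 6, 8, 10 and 12. The intervals ending at those visits are 1, 1, 2, 2, 2, 2 and 2 weeks. On schedule, the rule covers 2 of 7 post-baseline efficacy visits, weeks 1 and 2. Weeks 4 to 12 are counted in binges.

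**4. Size of the undercount on a literal reading.** Let d be binge days per week and r be binges per binge day (assumed). True binges per week are d × r, and the recorded value is d.
- Undercount = 1 - d/(d × r) = 1 - 1/r.
- Apparent step from week 2 to week 4 with no true change = (d × r)/d - 1 = r - 1.
- Shift in log(x + 1) at the entry minimum of d = 3, against a baseline counted in binges = ln(4) - ln(3r + 1).

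| r (assumed) | Undercount at weeks 1 and 2 | Week 2 to 4 step | Log shift at d = 3 |
|---|---|---|---|
| 1.0 | 0% | 0% | 0 |
| 1.5 | 33% | +50% | -0.32 |
| 2.0 | 50% | +100% | -0.56 |

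I take baseline as counted in binges. The opening paragraph defines the outcome over 2-week intervals, and the entry criterion covers the 2 weeks before baseline.

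**5. Early final visits.** A participant who stops for intolerable side effects has a final assessment, which may fall less than 2 weeks after the previous visit. If that visit counts as the endpoint for the response categories, an unchanged participant with r = 2 would show a 50% fall and be placed in the moderate category.

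**The case against.** The strongest reply has three parts.

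*The model settles the matter.* It states its response in binge days and labels the week 12 contrast the primary end point, in agreement with the endpoint section and the sample size. This is a good reason to resolve the conflict in favour of days. It does not remove the conflict: the opening paragraph under the same heading and two sentences of the secondary section say otherwise.

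*The short-interval sentence may be a slip.* It says the rate is estimated from binge days, not set equal to them, and the author may have meant scaling by the number of days in the interval. That is possible, so the undercount is conditional on a literal reading, and it is zero for anyone who never binges twice in a day. But no formula is given that would let an analyst recover another meaning.

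*The rule does little to the main result.* This stands for the planned week 12 value. A reader might infer that the rule biases the primary efficacy result. The documents do not support that: the modelled variable is binge days, which needs no conversion, and the scheduled week 12 value comes from a full 2-week interval. In the separate episodes model, early values could reach the week 12 estimate mainly through participants who drop out early.

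**Conclusion.** The point holds. Its main part is that the primary variable is stated two ways, which leaves a choice open after the data are seen and leaves the sample size justified for only one option. This rests on the text alone and needs no assumption.

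The short-interval rule is a secondary fault. Read literally, it lowers episode counts at weeks 1 and 2 by 0% to 50% for r from 1.0 to 2.0, and it changes the unit between weeks 2 and 4. Those percentages rest entirely on assumed values of r. The rule affects the early course of episodes and episode values from a final visit under 2 weeks after the last one.

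A reader might also infer that the trial is too small. This point does not show that: 40 per arm reproduces for binge days, and for episodes adequacy cannot be judged either way.

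**What to change.** 1. In the opening of Primary endpoint analysis and in the secondary list, name binge days per week (log-transformed, change to week 12) as primary and episodes per week as secondary. Correct the effect-size sentence that calls binges per week the primary analysis. The hypothesis, endpoint section, model and sample size then stand as they are.
2. Keep the 2-week window, including the 2 weeks before baseline, and state that baseline episodes are counted in binges.
3. Replace the short-interval sentence. When the interval is under 2 weeks:
   - binges per week = confirmed binges in the interval × 7 / days with diary or interview data in the interval;
   - binge days per week = binge days in the interval × 7 / the same number of days.

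The new formula should be confined to short intervals. Applying a since-last-visit average at every visit would, after a missed week 10 visit, spread the week 12 value over weeks 8 to 12 and so alter the primary endpoint. Dividing by days with data avoids counting unrecorded days as binge-free.

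The cost is a few sentences in the analysis section. Episodes are already to be identified in diaries and confirmed at interview, so no new data, visits or participants are needed, and the total stays at 80.
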